	All subjects who received at least one Therapeutic Dose of Ultratrace iobenguane I 131 will be included in the Full Analysis Set; all subjects who received both Therapeutic Doses and who attended the 3 Month and 6 Month Efficacy Visits with no major Protocol violations will be included in the Per Protocol Set. For each of these populations, a point estimate (with a 95% confidence interval, using the normal approximation with a continuity correction) for the proportion of subjects experiencing a reduction in use of all antihypertensive medication by at least 50% for at least six months or two cycles will be calculated. This single arm trial will be considered a

success if the lower limit of the two-sided 95% confidence interval for the Full Analysis Set exceeds 0.10 (10%).

Secondary analyses of the primary efficacy endpoint and analyses of the secondary efficacy endpoints will be conducted as described in the protocol and Statistical Analysis Plan.

Safety analyses will include treatment emergent adverse events, clinical laboratory measurements, vital signs measurements, and physical examination findings. Adverse events and incidence of overall toxicity, categorized by toxicity grades (severity), will be described. All subjects who received the Imaging Dose of Ultratrace iobenguane I 131 will be included in the analysis of any safety endpoint. Adverse events will be captured for all enrolled subjects and those prior to the Imaging Dose will be displayed in a separate listing.

Sponsor Contact Information

Main Telephone Number for Business Hours 8:30 AM – 5:00 PM EST	
Worldwide Safety Hotline	
MD Executive Vice President, Research & Development Medical Monitor	
Clinical Trial Manager	

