13. STATISTICAL METHODS

The detailed prospective procedures for data analysis are described in the Statistical Analysis Plan. Any changes in the original statistical methodology will be documented in the final Clinical Study Report. All statistical analyses, except those for dosimetry, will be performed using SAS[®] statistical analysis software version 9.1 or greater.³⁹

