13.3.2 Efficacy Analysis

13.3.2.1 Primary Analysis: Reduction in use of antihypertensive medication

The primary endpoint in this study is the proportion of subjects, after a Therapeutic Dose of Ultratrace iobenguane I 131, with a reduction (including discontinuation) of all antihypertensive medication by at least 50% for at least six months or two cycles. The duration of benefit is measured by maximum duration as follows. A benefit duration period commences when the subject's medication is reduced to a level at or below 50% of baseline, and continues until the subject's medication rises above 50% of baseline. For purposes of illustration, the following examples are provided (Month refers to the number of months after the first Therapeutic Dose).

- Example 1: A patient experiences the clinical benefit from the beginning of Month 2 to the beginning of Month 4, and then again from the beginning of Month 5 to the beginning of Month 12. Since the maximum duration of the benefit was 7 months, the subject is considered a success on the primary endpoint.
- Example 2: A patient experiences the clinical benefit from the beginning of Month 2 to the beginning of Month 4, and then again from the beginning of Month 6 to the beginning of Month 11. The patient begins another anticancer treatment at Month 15 and is discontinued. Even though the patient experienced the clinical benefit for a total of 7 months, the maximum duration of the benefit was only 5 months, so the subject is considered a failure on the primary endpoint.
- Example 3: A patient experiences the benefit from the beginning of Month 2 to the beginning of Month 9. At Month 10, the patient receives another anticancer treatment and is discontinued from the study. Since the maximum duration of the benefit was 7 months, prior to discontinuation, the patient is considered a success on the primary endpoint.

For the primary analysis of the primary endpoint, a point estimate (with a 95% confidence interval, using the normal approximation with a continuity correction) for the proportion of subjects experiencing a reduction (including discontinuation) of all antihypertensive medication

by at least 50% for at least six months or two cycles will be calculated. This single-arm trial will be considered a success if the lower bound of the two-sided 95% confidence interval exceeds 0.10 (10%). The Full Analysis Set will be used for the primary analysis, but this same analysis will be repeated for the Per Protocol Set.

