13.5 Procedures for Reporting Deviations to Original Statistical Analysis Plan

Any changes from the statistical analysis described in this Protocol will be documented in the final Statistical Analysis Plan. Any deviations from the final Statistical Analysis Plan will be provided in the final clinical study report.

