For the primary analysis of the primary endpoint, a point estimate (with a 95% confidence interval, calculated using the Agresti-Coull method) for the proportion of subjects in the Full Analysis Set with a reduction (including discontinuation) of all antihypertensive medications by at least 50% for at least six months or two cycles will be calculated. This single-arm trial will be considered a success if the lower bound of this two-sided 95% confidence interval exceeds 0.10 (10%).

A listing of response to treatment (yes/no) with supporting information (antihypertensive medications with their dates of use, doses and relative change from baseline) will be presented.

Use of antihypertensive medication over time will be presented graphically by subject. These figures will include the mean systolic and diastolic blood pressure measurements from healthcare providers (either at site visits or at the subject's home) for each visit window. This information will also be presented in a data listing.

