9. CHANGES FROM VERSION 1.0 OF SAP

The following are a summary of changes from those specified in Version 1.0 of the SAP (16 November 2009). Additional changes from Version 3.0 to 4.0 of this SAP are indicated at the end of this table.

Section	Version	Change
5.1	5.0	Clarification of handling of subjects with multiple enrollments
6	5.0	Removal of identification of per-protocol population
7.0	2.0	Time to event analyses added to statistical methods section.
7.0	5.0	Clarification of period definitions
7.2.4	2.0	New section added to reference imaging listings.
7.1	4.0	Addition of visit windows for summaries
7.3.1	2.0	Clarifications and additional details added to define algorithms for primary endpoint duration and for 50% reduction in antihypertensive medication use.
7.2.3.2	5.0	Update in MedDRA dictionary version
7.3.2	5.0	Update in WHO Drug Dictionary version
7.3.4	2.0	Listing of tumor response, clinical benefit status, and % change in CgA added.
7.3.6	2.0	Correlations between tumor change from baseline and tumor response, and among tumor markers added.
7.3.7	3.0	Section for tumor marker trend analysis deleted, all subsequent sections renumbered.
7.3.8	3.0	NIH Questionnaire reporting limited to reporting by item by visit.
7.3.9	2.0	Shift tables of pain medication use added. Comparisons of changes in potency using narcotic to NSAID conversions deleted.
7.3.11	2.0	Overall survival algorithm changed to reference date of first therapeutic dose as opposed to informed consent date.
7.3.12	2.0	New section added for site assessment of disease.
7.4.1	5.0	Definition of end of assessment period for subjects who terminate the study early, clarification of blood pressure measurements to be presented in figures by subject, clarification of clinical benefit period.
7.4.2	5.0	Added section with calculation of the primary endpoint, which was Appendix 1.
7.4.4	3.0	Threshold for reporting most frequent adverse events increased to 20% from 5%.
7.4.5	5.0	Clarification of objective tumor response criteria
7.4.7	5.0	Clarification of tumor marker analyses, change in correlation measures from percent change from baseline to tumor marker response, addition of a binary response comparison
7.4.8	5.0	Change in definition of baseline values
7.4.9	2.0	Added reporting for estimated creatinine clearance, including classification of values into estimates of renal function added.

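### The protocol and SAP apply the same primary success rule to different 95% intervals; the SAP's needs two fewer responders (11 rather than 13 of 58), and the SAP text available does not record the change

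*SAP*

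**What the plan says.** The set, the confidence level and the bar agree. Protocol Section 4 (Statistical Methods) and Section 13.3.2.1, and SAP Section 7.4.1, all take the Full Analysis Set and call the trial a success if the lower bound of the two-sided 95% interval is above 0.10.

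The interval itself does not agree:

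- Protocol 13.3.2.1, with the same words in the Section 4 outline: "using the normal approximation with a continuity correction".
- SAP 7.4.1: "a point estimate (with a 95% confidence interval, calculated using the Agresti-Coull method) for the proportion of subjects in the Full Analysis Set".

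On which document leads, Protocol Section 13 says "The detailed prospective procedures for data analysis are described in the Statistical Analysis Plan", and Protocol 13.5 says "Any changes from the statistical analysis described in this Protocol will be documented in the final Statistical Analysis Plan". SAP Section 9 describes itself differently: "The following are a summary of changes from those specified in Version 1.0 of the SAP". Its row for 7.4.1 begins "Definition of end of assessment period for subjects who terminate the study early, clarification of blood pressure measurements" and goes on to the benefit period. It does not mention the interval.

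Protocol 13.2 and SAP Section 6 give the design: null proportion 0.10, alternative 0.25, one-sided alpha 0.025, power 0.90, 58 subjects and about 75 enrolled. Protocol 13.2 ties the 58 to the Per Protocol Set.

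**The concern.** This interval is the trial's only efficacy decision rule. If two plausible results pass under one document and fail under the other, the criterion for success is not fixed until someone decides which document to follow. In an open-label, single-arm trial the pre-specified threshold is a main safeguard, and here the difference runs in the lenient direction with no reason given in the text available.

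A related point is that the stated 0.025 and 0.90 may not describe either rule as it will actually be applied.

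**Working it through.** **Inputs.** p0 = 0.10, p1 = 0.25, one-sided alpha 0.025, power 0.90 and n = 58 (Protocol 13.2, SAP 6); about 75 enrolled; bar 0.10; z = 1.96. The size of the Full Analysis Set is not given, so 58 to 75 (18 sizes) is assumed.

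**The plan's own figure.** The normal-approximation formula without continuity correction gives

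n = [(1.96·√(0.10·0.90) + 1.2816·√(0.25·0.75)) / 0.15]² = [(0.588 + 0.555) / 0.15]² = 58.06.

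The stated 58 is therefore reproduced, by a calculation that corresponds to neither interval.

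**Protocol limit.** L = p − 1.96·√(p(1−p)/n) − 1/(2n).

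- 11/58: 0.1897 − 0.1009 − 0.0086 = 0.080, fail.
- 12/58: 0.2069 − 0.1042 − 0.0086 = 0.094, fail.
- 13/58: 0.2241 − 0.1073 − 0.0086 = 0.108, pass.

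**SAP limit (Agresti-Coull).** ñ = n + z² = 61.84, p̃ = (x + z²/2)/ñ, L = p̃ − 1.96·√(p̃(1−p̃)/ñ).

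- 10/58: 0.1928 − 0.0983 = 0.094, fail.
- 11/58: 0.2089 − 0.1013 = 0.108, pass.
- 12/58: 0.2251 − 0.1041 = 0.121, pass.

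At n = 75 the limits, protocol against SAP, are 0.081 and 0.103 for 13 responders, and 0.092 and 0.113 for 14. The add-four form of Agresti-Coull gives the same counts at all 18 sizes.

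**Exact size and power.** Size is P(X ≥ x) at 0.10 and power is P(X ≥ x) at 0.25, with X binomial.

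| n | Protocol: needs | size | power | SAP: needs | size | power |
|---|---|---|---|---|---|---|
| 58 | 13 | 0.0042 | 0.722 | 11 | 0.0273 | 0.890 |
| 62 | 13 | 0.0076 | 0.809 | 11 | 0.0423 | 0.933 |
| 64 | 14 | 0.0038 | 0.761 | 12 | 0.0236 | 0.907 |
| 70 | 15 | 0.0035 | 0.794 | 13 | 0.0205 | 0.920 |
| 75 | 15 | 0.0068 | 0.873 | 13 | 0.0343 | 0.957 |

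Across all 18 sizes:

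- The gap is two responders at every size.
- The SAP rule's size is above 0.025 at 14 sizes, with a maximum of 0.0423 at n = 62. Its power is below 0.90 only at n = 58 and n = 63 (0.895).
- The protocol rule's power is below 0.90 at every size.
- Size at most 0.025 together with power at least 0.90 holds for the SAP rule at n = 64, 70 and 71 only, and for the protocol rule nowhere.

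**Chance of opposite verdicts.** This is P(x_SAP ≤ X < x_protocol).

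| True rate | n = 58 (X = 11 or 12) | n = 75 (X = 13 or 14) |
|---|---|---|
| 0.20 | 25.7% | 21.4% |
| 0.25 | 16.8% | 8.4% |
| 0.30 | 5.7% | 1.5% |

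**The case against.** The strongest reply is that the SAP governs and is unambiguous: one interval, one analysis set, one bar. Its rule also fits the stated design better. At n = 58 it has size 0.0273 and power 0.890 against the planned 0.025 and 0.90, whereas the protocol rule has power of only 0.722. That is a sound reason to prefer Agresti-Coull, and it stands. It supports keeping the interval; it does not show that the change was recorded.

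On the record, Protocol 13.5 does not ask for a date or a reason, and stating Agresti-Coull in SAP 7.4.1 might itself be called documentation. Section 9 tracks changes from SAP Version 1.0, so it would properly be silent if Agresti-Coull was already there. Protocol Section 13 also sends changes in methodology to the Clinical Study Report. These points have some weight: date and reason are good practice rather than a protocol requirement, and the silence of Section 9 says nothing about when the interval changed. But 13.5 places changes from the protocol analysis in the SAP specifically, and nothing in the SAP text available tells the reader that 7.4.1 departs from 13.3.2.1.

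On size and power, 0.025 and 0.90 are described as the basis of the sample size, not as a guarantee of exact error control, and part of the variation over 58 to 75 is binomial discreteness. That is fair. The figures are still the only operating characteristics given, and neither rule meets both at most sizes.

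Finally, the verdict differs at only two counts, and at n = 75 with a true rate of 0.30 the chance of a split is 1.5%. That is true, but at true rates of 0.20 to 0.25 it is 8.4% to 25.7%.

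**Conclusion.** The concern holds. The two documents state the same primary success rule on different intervals, and the SAP's version needs two fewer responders at every Full Analysis Set size from 58 to 75. The SAP probably governs. If so, the primary decision rests on a more lenient limit than the protocol states, with an exact size slightly above 0.025 at n = 58 and further above it at some other sizes.

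This rests on three assumptions:

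- The Full Analysis Set lies between 58 and 75.
- The protocol phrase has its ordinary meaning, the estimate minus z standard errors minus 1/(2n). A continuity-corrected score interval would narrow the gap to 0 or 1, but neither document names one.
- No SAP page missing from the text available records the change.

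No late switch is claimed. The protocol is dated 21 March 2014 and this SAP was written after enrolment closed in December 2015, but Agresti-Coull may have been in the SAP from Version 1.0.

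**What to change.** Before database lock:

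1. Name one interval as the decision rule in both documents. If the protocol is not reissued, the SAP entry should say that it supersedes both Section 13.3.2.1 and the Section 4 outline.
2. Record the interval in the SAP as a change from Protocol 13.3.2.1, in line with 13.5, and add the date and reason as good practice.
3. In place of the nominal 0.025 and 0.90, give the exact size and power of the chosen rule at the actual Full Analysis Set size. The nominal figures can remain as the basis on which 58 was planned.

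Keeping Agresti-Coull is acceptable on these terms, for example with 0.0273 and 0.890 reported at n = 58, or 0.0343 and 0.957 at n = 75. The cost is one SAP entry, aligned wording and restated figures, with no extra patients and no change to the SAP bar.

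Only if the sponsor wants one-sided 0.025 held strictly, the Clopper-Pearson lower limit would do it: 12 of 58 (size 0.0112, power 0.817) or 14 of 75 (0.0159, 0.923). That would be a third rule found in neither document. It raises the SAP bar by one responder at 14 of the 18 sizes and leaves power below 0.90 at 11 of them.

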6. DETERMINATION OF SAMPLE SIZE

The planned sample size for this study is 58 subjects, for which it is estimated that approximately 75 subjects may be enrolled. The one-sided alternative hypothesis of the study is that the proportion of subjects experiencing a reduction (including discontinuation) of all antihypertensive medications by at least 50% for at least six months or two cycles is 0.25, against the null hypothesis that the proportion is 0.10. Sample size was based on a one-sided significance level of $\alpha = 0.025$ and power of 0.90 (90%).

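### The SAP's Agresti-Coull success rule is approximate: its exact one-sided type I error can exceed the stated 0.025 (0.027 at n = 58, up to 0.042 over an assumed n of 58 to 75), and the SAP does not say so.

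*SAP*

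**What the plan says.** SAP 6 sets an alternative responder proportion of 0.25 for the primary endpoint, "against the null hypothesis that the proportion is 0.10". On the error rate it says: "Sample size was based on a one-sided significance level of" 0.025, with power 0.90. On numbers it says: "The planned sample size for this study is 58 subjects, for which it is estimated that approximately 75 subjects may be enrolled". Protocol 13.2 gives the same level, power and hypotheses, and ties the 58 to the Per Protocol Set.

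SAP 7.4.1 estimates the proportion in the Full Analysis Set "with a 95% confidence interval, calculated using the Agresti-Coull method". The trial succeeds if the lower bound of that two-sided 95% interval is above 0.10.

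Protocol 13.3.2.1 has the same 10% threshold and the same analysis set, but uses a normal-approximation interval with a continuity correction. Neither document gives the responder count needed for success or the exact type I error of its rule.

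**The concern.** A two-sided 95% interval whose lower limit must clear 0.10 looks like a one-sided test at 0.025. That equivalence is exact only when the limit comes from inverting the exact binomial test. The Agresti-Coull limit is an approximation. With 58 to 75 subjects and a true rate of 0.10, the smallest successful count can have a null probability above 0.025.

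This is an open-label, single-arm trial with one success criterion, so the false-success rate of this rule is the false-success rate of its only confirmatory claim. The issue is separate from the protocol and SAP naming different intervals: it would remain if the protocol were changed to match the SAP.

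**Working it through.** **Inputs.** Null 0.10, alternative 0.25, one-sided level 0.025, power 0.90, 58 planned and about 75 enrolled (SAP 6). Primary analysis in the Full Analysis Set (SAP 7.4), which requires at least one Therapeutic Dose (SAP 5.3).

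**Assumed range.** The Full Analysis Set contains the Per Protocol Set and cannot exceed the number enrolled. If both targets are met, it lies between 58 and 75. The documents do not give its size.

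**The plan's own figure.** The one-sample normal approximation gives

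n = [(1.960·√(0.10·0.90) + 1.282·√(0.25·0.75)) / 0.15]² = 58.06,

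which agrees with the stated 58.

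**The SAP rule.** With z = 1.96, ñ = n + z² and p̃ = (x + z²/2)/ñ, the lower limit is p̃ − z·√(p̃(1 − p̃)/ñ).

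For n = 58, ñ = 61.84:
- x = 10: p̃ = 11.92/61.84 = 0.1928, lower limit 0.094, not a success.
- x = 11: p̃ = 12.92/61.84 = 0.2089, lower limit 0.2089 − 1.96·0.0517 = 0.108, a success.

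The cut-off is 11, and the exact type I error is P(X ≥ 11 | n = 58, p = 0.10) = 0.0273. The Clopper-Pearson lower limit for 11/58 is 0.099, so that count fails the exact 0.025 test.

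**All sizes from 58 to 75.** The cut-off is the smallest successful count. Type I error is exact at p = 0.10 and power is exact at p = 0.25.

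| n | SAP cut-off | SAP type I error | SAP power | Exact-limit cut-off | Exact-limit type I error | Exact-limit power |
|---|---|---|---|---|---|---|
| 58 | 11 | 0.0273 | 0.890 | 12 | 0.0112 | 0.817 |
| 59 | 11 | 0.0306 | 0.903 | 12 | 0.0128 | 0.836 |
| 60 | 11 | 0.0342 | 0.914 | 12 | 0.0146 | 0.852 |
| 61 | 11 | 0.0381 | 0.924 | 12 | 0.0165 | 0.868 |
| 62 | 11 | 0.0423 | 0.933 | 12 | 0.0187 | 0.882 |
| 63 | 12 | 0.0211 | 0.895 | 12 | 0.0211 | 0.895 |
| 64 | 12 | 0.0236 | 0.907 | 12 | 0.0236 | 0.907 |
| 65 | 12 | 0.0264 | 0.917 | 13 | 0.0113 | 0.860 |
| 66 | 12 | 0.0295 | 0.927 | 13 | 0.0128 | 0.874 |
| 67 | 12 | 0.0327 | 0.935 | 13 | 0.0145 | 0.887 |
| 68 | 12 | 0.0362 | 0.943 | 13 | 0.0163 | 0.899 |
| 69 | 12 | 0.0400 | 0.950 | 13 | 0.0183 | 0.910 |
| 70 | 13 | 0.0205 | 0.920 | 13 | 0.0205 | 0.920 |
| 71 | 13 | 0.0228 | 0.929 | 13 | 0.0228 | 0.929 |
| 72 | 13 | 0.0254 | 0.937 | 14 | 0.0112 | 0.892 |
| 73 | 13 | 0.0281 | 0.945 | 14 | 0.0126 | 0.904 |
| 74 | 13 | 0.0311 | 0.951 | 14 | 0.0142 | 0.914 |
| 75 | 13 | 0.0343 | 0.957 | 14 | 0.0159 | 0.923 |

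The SAP rule is above 0.025 at 58–62, 65–69 and 72–75, which is 5 + 5 + 4 = 14 of 18 sizes. It holds the level at 63, 64, 70 and 71. The version of Agresti-Coull that adds two successes and two failures gives the same cut-offs.

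**Just below the range.** The SAP rule is within 0.025 at n = 55 to 57 and above it at 51 to 54.

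**The protocol's interval.** The continuity-corrected normal interval needs 13/58 (error 0.0042, power 0.722) or 15/75 (error 0.0068, power 0.873). Its error lies between 0.003 and 0.008 over the whole range.

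**The case against.** The 0.025 can be read as a nominal level. SAP 6 says the sample size was based on it, and the 58 comes from a normal-approximation formula, so the design is approximate throughout. The score z-test that matches this formula also needs 11/58. Over 58 to 75 its cut-offs equal the Agresti-Coull cut-offs at 16 sizes, and at 63 and 70 Agresti-Coull is the stricter. The SAP rule is therefore no looser than the test behind the sample size. This stands, and it rules out calling the method an error.

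The excess is also often small: five of the 14 values are below 0.030, and the planned 58 is over by 0.0023. This stands too.

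Requiring an exact test would miss another stated property. Its power at 0.25 is below 90% at 11 of the 18 sizes (58–63, 65–68 and 72), whereas the SAP rule falls below 90% only at 58 and 63. So a switch to Clopper-Pearson is a trade-off and cannot be presented as a plain correction.

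Finally, returning to the protocol's interval would remove the excess altogether. That is true, but it costs more power still (72.2% at n = 58).

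None of this answers the remaining point. The SAP states 0.025 without saying that it is nominal and without giving the error of the rule that decides success.

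**Conclusion.** The concern holds as a should-fix. The only success rule does not reliably deliver the one-sided 0.025 level in SAP 6. If the Full Analysis Set has 58 to 75 subjects, the exact error is 0.0205 to 0.0423 and exceeds 0.025 at 14 of 18 sizes. At each of those 14, exactly one responder count succeeds under the SAP and fails the exact 0.025 test.

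A reader might infer that the trial's error is in fact inflated, or that 14 of 18 is the chance that it is. The documents do not support either inference. The set size is not given, 58 to 75 is inferred from targets, and at 55–57, 63, 64, 70 or 71 the rule complies. The maximum of 0.0423 belongs to one size, 62.

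A reader might also infer that the exact test is obligatory. Neither document promises exact control, and the exact rule often misses the stated power.

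**What to change.** 1. In SAP 6 and 7.4.1, state the responder cut-off, exact one-sided type I error at 0.10 and exact power at 0.25 for the actual Full Analysis Set. SAP 4.1 says enrollment was completed in December 2015, so the size can be determined. Say that 0.025 is nominal if that is what is meant.
2. Report the exact binomial p-value and Clopper-Pearson lower limit beside the Agresti-Coull result. A success resting on a count such as 11/58 (limits 0.108 and 0.099) is then visible.
3. If strict control at 0.025 is intended, base the decision on the exact lower limit and keep Agresti-Coull for display. Restate the power: 81.7% at 58, 89.9% at 68 and 92.3% at 75.
4. Reconcile the interval with Protocol 13.3.2.1 in the same revision. Protocol 13.5 already requires changes from its analysis to be documented in the final SAP.

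Items 1 and 2 cost a few lines of text and one extra output, and leave the decision rule unchanged. Item 3 asks for one more responder at 14 of the 18 sizes and none at the other four. It should be settled before database lock.
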